8.3.2 Vital Signs

Vital signs include assessment of heart rate, respiratory rate, body temperature (aural measurement), and BP. Vital signs will be taken with the participant in the supine position after resting for at least 5 minutes, at the times indicated in the SoA (Section 1.3).

8.3.3 Electrocardiograms

Triplicate standard 12-lead ECGs will be obtained after the participant has been in a supine position for at least 5 minutes at times indicated in the SoA (Section 1.3). The ECGs will be

measured using standardized equipment provided by a central core laboratory. The ECGs will be assessed by central review and a report provided to the site. Results from Screening ECG must be either normal or reveal findings deemed not to be of clinical significance by the Investigator for the participant to qualify for the study. CCI

8.3.4 Columbia-Suicide Severity Rating Scale (C-SSRS)

The C-SSRS is a standardized clinician-reported outcome tool used to assess suicidal risk status of the participant that can be administered by trained non-mental health personnel. The assessment is completed based on participant responses. The C-SSRS should be completed before other types of study procedures, such as blood draws and physical examinations, are performed. Suicidality will be monitored throughout the study employing a validated questionnaire C-SSRS. The C-SSRS will be completed at each site visit as indicated in the SoA (Section 1.3) and the results must be evaluated by the Investigator to recommend any additional intervention, if needed. Based on determination of positive C-SSRS results for suicidality, the participants will be discontinued from the study medication and referred to a specialist at the Investigator's discretion for further evaluation. CCI

CCI

CCI

8.3.7 Clinical Safety Laboratory Tests

CCI, clinical chemistry, urinalysis, serology, and additional laboratory parameters to be tested during the study are listed in [Appendix 3](#). At Screening and the EOS Visit, participants are required to be in a fasted state at the time of the laboratory sample (with fasting defined as at least 8 hours following the last meal or snack). At all other scheduled visits, participants do not need to be in a fasted state; however, fasting status will be documented. At least 1 backup aliquot at each visit will be stored for potential further assessments.

Laboratory samples will be analyzed by a central laboratory. Laboratory tests may be repeated at any visit if there was an abnormal finding at the most recent previous evaluation or if additional information is clinically necessary to appropriately evaluate the participant's current condition, follow-up, and/or manage an AE.

The Investigator will review laboratory results with a frequency that ensures participants safety. Clinically significant changes from Screening in laboratory results must be considered

an AE and recorded in the eCRF. Clinical significance is defined as any variation in a laboratory result that has medical relevance and that results in a change in medical care. The Investigator will continue to monitor the participant until the finding is resolved or, in the judgment of the Investigator, follow-up is no longer medically necessary.

Local assessment of clinical laboratory parameters is permitted when these data are required for safety reasons in a timeframe faster than the central laboratory can provide.

Specific withdrawal criteria for liver enzymes are presented in the Withdrawal Section 7.0.

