1.3 Schedule of Activities

Study Period	Screening			Randomization and Treatment Period					Safety Follow-up		Discontinuation	
	CCI											
	CCI											
Window (days)	CCI											
Timing		Start of SC	Start of BC	Start of TRC1	CCI	Start of TRC2	Start of TRC3	Start of SFC	Day 14 after stopping intake of study medication	End of the SFC		
Informed Consent	X ^b											
Inclusion, Exclusion/Eligibility criteria	X	X	X	X ^c								
Demographics	X											
Medical History (includes current condition, eg, documentation of surgical diagnosis of endometriosis ^d)	X											
Gynecological History	X											
Prior/Concomitant Medications	X	X	X	X	X	X	X	X	X	X	X	

Study Period	Screening			Randomization and Treatment Period				Safety Follow-up			Discontinuation
CCI	CCI										
Window (days)	CCI										
Full Physical Examination (including height and weight)	X							X			X
Focused Physical Examination (Cardiac, Respiratory, GI)				X	X		X			X	
Gynecological Examination ^e / Contraception Counseling ^f	X							X		X	X
Rescue Medication Dispensing and Instructions for Use		X	X	X	X		X	X			
Home UPT Dispensing ^g	X		X	X							
Treatment Allocation				X							
CCI			X								
				X ^h	X ⁱ		X				
OG-6219/Placebo Accountability				X ^h	X		X	X			X
Dispense/Collect eDiary		X	X	X						X	X

Study Period	Screening	Randomization and Treatment Period						Safety Follow-up	Discontinuation	
CCI	CCI							CCI		
Window (days)	CCI									
eDiary Training/Re-training ^j		X	X	X	X		X	X		
eDiary Compliance ^k			X	X	X	X	X	X	X	
eDiary CCI										
				■				■		
Patients' Impression of Change (PGI-C) ¹						X	X	X		
Patients' Impression of their Overall Severity (PGI-S) ¹				X		X	X	X		

Study Period	Screening			Randomization and Treatment Period				Safety Follow-up			Discontinuation
CCI											
Window (days)	CCI										
Vital Signs (Heart Rate, Blood Pressure, Respiratory Rate, Temperature)	X	X	X	X	X		X	X		X	
12-Lead ECG	X			X ^m	X ^m		X ^m	X		X	X
Clinical Laboratory Tests (Hematology and Chemistry panels) ^a	X			X	X		X	X		X	X
Urinalysis	X			X	X		X	X		X	X
STI Panel ^o	X										
UPT ^p	X	X	X	X	X	X	X	X		X	X
Serum Pregnancy Test (β-hCG) ^q	X		X	X	X		X	X		X	X
CCI											
AE	X	X	X	X	X	X	X	X	X	X	X

Study Period	Screening			Randomization and Treatment Period					Safety Follow-up			Discontinuation
CCI	CCI					CCI	CCI					
Window (days)	CCI											
Plasma PK Sampling ^u											X	
CCI												
Columbia-Suicide Severity Rating Scale (C-SSRS) ^{1,7}	X	X	X	X	X		X	X		X	X	

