In this Phase 2a/b 4-arm PoC, dose-range study, treatment over CCI is intended to assess the effect of treatment with OG-6219 on efficacy, safety, and tolerability over 6 menstrual cycles.

While a previous study in cynomolgus monkeys exposed to OG-6219 for a total of CCI did not find any statistically significant changes in the mean CCI. An increase CCI in this Phase 2a/b study, if any, is expected to be fully and quickly reversible.

CCI

Also, no macroscopic or microscopic effect on bone tissue was observed in the CCI toxicology studies in rat and cynomolgus monkeys. However, no clinical experience on the effect of OG-6219 on systemic estrogen levels with longer exposure is available.

CCI

Effects on coagulation and lipid parameters as well as cardiovascular function will be monitored by serum chemistry, vital signs, and ECGs.

Participants will need to stop using any previous hormonal treatment for endometriosis as well as oral and other contraceptive treatment to enable assessment of the effect of HSD17 β 1 inhibition by OG-6219 on ERP, and menstrual regularity of the endometrium (refer to the [Table 2](#) and [Appendix 7](#)).

Embryo-fetal survival and development during the organogenesis phase of pregnancy was studied in pregnant rats and cynomolgus monkeys and no effect of OG-6219 treatment was found at the respective highest doses tested. However, as the effect of OG-6219 on fertility and early embryonic development and pre- and post-natal development has not been studied at this time, the risk of reproductive toxicity cannot be considered fully characterized. Therefore, necessary precautions to prevent pregnancy will be taken in this study. Participants will be informed about the risks to become pregnant and should not plan to become pregnant over the course of the study; only participants who are abstinent, or who are willing to reliably use an acceptable effective method for contraception as described in detail in the protocol (refer to the [Appendix 5](#)) and informed consent, or in whom safe contraception is achieved by a permanent method, will be eligible. A negative serum β -human chorionic gonadotropin (β -hCG) test prior to randomization and start of the treatment will be required, and monthly urinary pregnancy tests will be performed during the study implementation. Any pregnancy

will trigger withdrawal from study treatment, participant to expedited reporting and outcome of the pregnancy will be followed.

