8.4.1 Time Period and Frequency for Collecting AE and SAE Information

All AEs and SAEs will be collected from the signing of the ICF until EOS at the time points specified in the SoA (Section 1.3).

All SAEs will be recorded and reported to the Sponsor or designee immediately and under no circumstance should this exceed 24 hours of the Investigator's awareness of the event, as indicated in Appendix 4. The Investigator will submit any updated SAE data to the Sponsor or designee within 24 hours of their awareness of the updated information.

From the time of screening (V1) through EOS/discontinuation, which is 30 days after last intake of study treatment, all AEs, SAEs, and other reportable safety events must be reported by the Investigator.

Additionally, any SAE brought to the attention of an Investigator at any time outside the period specified in the previous paragraph must be reported immediately (within 24 hours of learning about the event) to the Sponsor if the event is considered related to study treatment.

Investigators are not obligated to actively seek information on AEs or SAEs after conclusion of the study participation. However, if the Investigator learns of any SAE, including a death, at any time after a participant has been discontinued from the study, the event/cause of death is considered to be reasonably related to the study treatment or study participation, the Investigator must promptly notify the Sponsor or designee.

All initial and follow-up AEs, SAEs, and other reportable safety events will be recorded and reported to the Sponsor or designee within the time frames as indicated in Table 7.

The method of recording, evaluating, and assessing causality of AE and SAE and the procedures for completing and transmitting SAE reports are provided in Appendix 4.

Table 7 Reporting Time Periods and Time Frames for Adverse Events and Other Reportable Safety Events

Type of Event	Reporting Time Period: Screening (V1) to Pre-Treatment Allocation (C)	Reporting Time Period: Treatment Allocation (C) through Protocol-specified Follow-up Period	Time Frame to Report Event and Follow-up Information to Sponsor:
Nonserious Adverse Event (NSAE)	Report if: 
 Due to protocol-specified procedure Causes exclusion 	Report all	Per data entry guidelines

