Appendix 3 Clinical Laboratory Tests

The tests detailed in Table 9 will be performed by the central laboratory. Local laboratory results are only required in the event that the central laboratory results are not available in time for either study treatment administration and/or response evaluation. If a local sample is required, it is important that the sample for central analysis is obtained at the same time. Additionally, if the local laboratory results are used to make either a study treatment decision or response evaluation, the results must be entered into the eCRF.

Protocol-specific requirements for inclusion or exclusion of participants are detailed in Section 5.0 of the protocol.

Additional tests may be performed at any time during the study as determined necessary by the Investigator or required by local regulations.

All study-required laboratory assessments will be performed by a central laboratory.

The results of each test must be entered into the eCRF. Investigators must document their review of each laboratory safety report.

Additional tests may be performed at any time during the study as determined necessary by the Investigator or required by local regulations. Re-test of samples due to cancelled tests is permitted.

Table 9 Protocol-required Safety Laboratory Tests

Laboratory Assessments	Parameters
Hematology	Platelet count
	Red blood cell count
	Hemoglobin
	Hematocrit
	CCI
	Red blood cell indices:
	Mean corpuscular volume (MCV)
	Mean corpuscular hemoglobin (MCH)
	Mean cell hemoglobin concentration (MCHC)
	Red Cell Distribution Width (RDW)
	%Reticulocytes
	White blood cell count with differential (% and absolute):
	Neutrophils
	Lymphocytes
	Monocytes
	Peripheral smear
	Eosinophils
	Basophils
	Coagulation tests
	Prothrombin time
	Activated partial thromboplastin time
	Antithrombin III

Laboratory Assessments	Parameters	
Clinical Chemistry ^b	Blood urea nitrogen (BUN)	Aspartate aminotransferase (AST)/Serum glutamic-oxaloacetic transaminase
	Creatinine	Alanine aminotransferase (ALT)/serum glutamic-pyruvic transaminase
	Glucose (Fasting)	Alkaline phosphatase (ALP)
	Gamma glutamyl transferase (GGT)	Creatine kinase
	Urea	Creatine kinase MB fraction will be performed if clinically indicated
	Magnesium	Chloride
	Cholesterol	Globulin
	Potassium	Amylase
	Sodium	Total bilirubin
	Calcium	Conjugated and unconjugated bilirubin
	Lactate dehydrogenase (LDH)	Total protein
	Albumin	Phosphate
	Uric acid	Potassium

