### 8.1.3. Baseline and Change from Baseline

Baseline is defined as the last non-missing measurement (including unscheduled assessments) taken prior to first dose of randomized study medication (reference start date).

In the case where the last non-missing measurement and the reference start date coincide, that measurement will be considered pre-baseline with the following exceptions:

Adverse Events (AEs) and medications commencing on the reference start date will be considered as either pre-baseline or post-baseline based on the collected eCRF assessment of whether the item started prior to the start of study medication.

Visit 4 measurements scheduled to be made after first dose of randomized study medication (e.g. post-dose ECG measurements) will be regarded as post-baseline. Baseline ECG is the average of the triplicates taken prior to first dose of randomized study medication.

For related assessments (e.g., systolic and diastolic blood pressure), it is desirable that all baseline values come from the same measurement date and not from different dates/visits in case one value is missing. In the event where one value is missing, values from the same measurement dates will be used.

For HRQoL, Fatigue, and Productivity Questionnaires (EHP-30, EQ-5D-5L, WPAI-Endometriosis, PROMIS Fatigue Short Form 6a, and PGI-S) assessments collected on CCI will be considered Baseline. In case data were not entered CCI but within a few days from visit 4, these data will still be considered as baseline.

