### 8.7.2. Laboratory Evaluations

Quantitative laboratory measurements reported as '< X', i.e., below the lower limit of normal (LLN), or '> X', i.e., above the upper limit of normal (ULN), will be converted to X for the purpose of quantitative summaries, but will be presented as recorded, i.e., as '< X' or '> X' in the listings. If local and central laboratory assessments are available from the same day, central laboratory assessments will be used in the summary.

The following summaries will be provided for laboratory data:

- Observed values and change from baseline by visit for Chemistry, Hematology and Urinalysis (quantitative measurements)
- Observed values for categorical measurements
- Shift from baseline value to each post-baseline visit value according to normal range criteria (quantitative measurements and categorical measurements)

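### No on-treatment glucose sample has to be fasted, and the baseline-to-EOS laboratory change compares a sample of uncontrolled meal status with a fasted, off-drug one

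*Protocol*

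**What the plan says.** **Fasting rule.** Protocol 8.3.7 states: "At Screening and the EOS Visit, participants are required to be in a fasted state at the time of the laboratory sample". For the remaining visits it adds: "At all other scheduled visits, participants do not need to be in a fasted state; however, fasting status will be documented". Protocol 8.4.1 places EOS by the phrase "which is 30 days after last intake of study treatment".

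**Analytes.** Table 9 in Appendix 3 lists "Glucose (Fasting") under clinical chemistry, with no visit attached. Cholesterol is also in the chemistry list. LDL, HDL and triglycerides appear under other tests. Protocol 2.3.1 says: "Effects on coagulation and lipid parameters as well as cardiovascular function will be monitored by serum chemistry, vital signs, and ECGs".

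**Schedule.** The row "Clinical Laboratory Tests (Hematology and Chemistry panels") in the Schedule of Activities has samples at Screening, randomization, one visit during Treatment Cycle 1 (TRC1), the start of TRC3, the start of the Safety Follow-up Cycle (end of treatment, EOT), the end of that cycle (EOS), and discontinuation.

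**Analysis.** SAP 8.1.3: "Baseline is defined as the last non-missing measurement (including unscheduled assessments) taken prior to first dose of randomized study medication (reference start date"). Protocol 9.4.7 counts scheduled randomization-day assessments as pre-treatment, so the baseline is normally the randomization sample. SAP 8.7.2 plans: "Observed values and change from baseline by visit for Chemistry, Hematology and Urinalysis (quantitative measurements"), and shift tables by normal range from baseline to each later visit. The synopsis lists changes in laboratory abnormalities from baseline to EOS in its primary safety analysis. Neither SAP section mentions fasting status.

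**The concern.** Glucose and triglycerides depend on whether the woman has eaten. A change score is interpretable only if meal status is the same at both ends, or is known and used.

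Here the only post-baseline sample that must be fasted is taken a month after the drug has stopped, and it is compared with a baseline that need not be fasted. While women are on drug, any sample may be fed or fasted. The status is recorded but the analysis does not use it.

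Laboratory abnormalities are a primary safety endpoint. At stake is whether a within-arm change or a Normal-to-High shift in glucose can be read as a drug signal, and whether a modest real effect would show above the meal noise. The Table 9 label also suggests fasted glucose at every draw, which 8.3.7 does not require.

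**Working it through.** The plan gives no figure to reproduce on this point. The check is a count of samples, followed by an illustration with stated assumptions.

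**Count.** Schedule of Activities chemistry row against the rule in 8.3.7:

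| Sample | Drug status | Fasting required |
|---|---|---|
| Screening (V1) | before drug | yes |
| Randomization | pre-dose | no |
| Visit during TRC1 | on drug | no |
| Start of TRC3 | on drug | no |
| Start of follow-up (EOT) | end of treatment | no |
| End of follow-up (EOS) | 30 days after last dose | yes |
| Discontinuation | early stop | no |

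Fasting is required at 2 of 7 time points, and at 0 of the 3 scheduled treatment-period samples after randomization.

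**Illustration.** Let f be the share of samples taken fed where fasting is optional, and D the mean fed-minus-fasted difference for an analyte. Neither is in the documents, so f is shown at 0.25, 0.50 and 0.75 and results are in units of D. Suppose that samples required to be fasted are fasted, and that f and D are the same in all arms.

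- *EOS minus randomization baseline.* EOS has no fed samples, so the spurious mean change is 0 - fD = -fD. The added SD is D x sqrt(f(1 - f)).
- *On-treatment minus randomization baseline.* With the same f at both visits the mean shift is fD - fD = 0. With fasting state independent between visits, the added SD is D x sqrt(2f(1 - f)).

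| f | EOS: mean shift | EOS: added SD | On treatment: mean shift | On treatment: added SD |
|---|---|---|---|---|
| 0.25 | -0.25D | 0.43D | 0 | 0.61D |
| 0.50 | -0.50D | 0.50D | 0 | 0.71D |
| 0.75 | -0.75D | 0.43D | 0 | 0.61D |

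If each woman keeps the same habit at every optional visit, the on-treatment noise shrinks towards zero. The EOS shift does not.

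- *Active minus placebo at EOS.* (-fD) - (-fD) = 0. The mismatch sits in the pre-dose sample, so randomization alone makes it equal in expectation.
- *On-treatment minus Screening.* Protocol 8.3.7 judges clinically significant laboratory changes for adverse-event recording against Screening, a fasted reference. The mismatch then runs the other way, fD - 0 = +fD, again alike in all arms.

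**The case against.** The strongest reply is that this is a disclosed design choice with a concurrent control. Protocol 9.4.1 presents summaries by treatment group, so placebo stands beside each dose and should show the same artefact. The randomization baseline and the treatment-period samples follow one rule, so there is no built-in on-treatment mismatch. All of this stands, and it limits the point to distorted within-arm readings and lost sensitivity.

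A reader might infer more than the documents support:

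- *That no placebo comparison removes the artefact.* No formal laboratory test against placebo is planned, but the descriptive comparison is there and is unbiased in expectation.
- *That the SAP pools fasted and fed visits.* Its tables are by visit, so EOS is shown separately from the on-treatment visits.
- *That secondary safety endpoint 9 compares fasted V1 with a fed end-of-treatment sample.* Its end visit is redacted. The endpoint also rests on medical relevance rather than range flags, and the investigator can take documented fasting status into account.
- *That the same count applies to LDL, HDL and triglycerides.* Their visits cannot be read, so the point covers lipids only where they are drawn at the visits concerned.
- *That Protocol 2.3.1 promises fasted lipids.* It promises monitoring and says nothing about fasting.
- *That no fasted on-treatment values will exist.* Some women may attend fasted. The documents support only that samples can be mixed.

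The reply is also right that Screening should not replace baseline for everyone. That would depart from the protocol's safety baseline and move it back by about 56 to 92 days (14 + 21 + 21 to 28 + 32 + 32, from the stated initial period and two cycles).

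**Conclusion.** The point holds in this form. No on-treatment sample has to be fasted, and the planned baseline-to-EOS change and shift in glucose has a built-in meal-status mismatch, as it does for lipids where they are drawn at those visits. On-treatment changes are uncontrolled at both ends, so they are noisier but not systematically shifted. The comparison with placebo is not biased.

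The size is -fD at EOS in every arm, and up to about 0.71D of added SD on treatment. The absolute size is unknown because the documents give neither f nor D. The conclusion assumes that baseline is usually the randomization sample, that the fasting rule is followed where it applies, and that meal habits at optional visits do not differ by blinded arm.

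This is a worthwhile, low-cost improvement to a primary safety output. It does not affect the efficacy analysis. The Table 9 label is a separate wording conflict with 8.3.7. It is a test name and creates no visit rule, but the two passages must be reconciled.

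**What to change.** In SAP 8.7.2, keep the planned laboratory tables and add for glucose and lipids:

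1. Observed values by visit, treatment group and documented fasting status.
2. Change and shift from fasted pairs only. The baseline for these tables is the last documented-fasted value before the first randomized dose: the randomization sample if fasted, otherwise Screening.
3. A label marking these tables as supplementary, with the number of fasted pairs per arm and visit.

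Reconcile Table 9 in Appendix 3 with Protocol 8.3.7 so that the reader knows which glucose values are fasted.

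The cost is SAP wording, some programming and one variable that the protocol already says is documented; confirm that it reaches the analysis database. The fasted tables will have fewer samples. The subset is also selected on fasting status after randomization, so arms may be less comparable in it, which is why it should supplement the planned tables and not replace them. No new data are needed. A required fasted on-treatment sample would need a protocol amendment. With a SAP dated June 2025, and full enrolment already projected in the February 2024 amendment, that is probably too late and is not part of this recommendation.
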